1.1. Synopsis

Protocol Title:	Multicenter, open-label, phase 1 study investigating the safety and tolerability of encorafenib monotherapy in BRAF V600E-mutated Chinese patients with advanced metastatic solid tumors (OCEAN I study)
Short Title:	Phase 1 safety study of encorafenib in Chinese patients with advanced metastatic BRAF V600E mutant solid tumors
Rationale:	
B-RAF proto-oncogene, serine/threonine kinase (BRAF) mutations, which lead to constitutive activation of BRAF kinase and sustained rat sarcoma viral oncogene homologue (RAS)/proto-oncogene serine/threonine-protein kinase (RAF)/mitogen-activated protein kinase kinase (MEK)/extracellular signal-related kinase (ERK) pathway signaling resulting in increased cell proliferation and survival occur in approximately 25% of melanomas and 0.5 to 2.8% of non-small cell lung cancer (NSCLCs) in China. These data also showed that the V600E mutation was the most frequent BRAF mutation in both melanoma and NSCLC (89% and 32 to 86%, respectively).
 
In real-world setting and clinical studies, melanoma and NSCLC patients with a B-RAF proto-oncogene, serine/threonine kinase V600E (BRAF V600E) mutation have unfavorable clinical outcome when treated with chemotherapy and immunotherapy compared to non-BRAF V600E and/or BRAF wild-type patients. Poor clinical outcome with chemotherapy has also been reported in Chinese populations.
 
Encorafenib inhibits BRAF kinase, thereby inhibiting B-RAF proto-oncogene, serine/threonine kinase V600 (BRAF V600) positive cell growth. Encorafenib is registered in combination with the MEK inhibitor binimetinib in several jurisdictions for the treatment of patients with unresectable or metastatic melanoma with a BRAF V600E or BRAF V600K mutation, based on results from the phase 3 COLUMBUS study [Dummer 2018a, Dummer 2018b]. It could therefore be anticipated that the efficacy of encorafenib in combination with binimetinib in other BRAF V600 driven cancer types such as BRAF V600E mutant NSCLC may be similar than that observed with the combination of dabrafenib and trametinib.
 
Tumor regression has been shown with encorafenib and binimetinib monotherapy in a BRAF-mutant human NSCLC xenograft model, and enhanced tumor regression was observed with the combination of encorafenib plus binimetinib. In a human xenograft melanoma mice model, encorafenib plus binimetinib combination treatment has delayed the emergence of resistance due to RAS/RAF/MEK/ERK pathway reactivation.
 
The safety and tolerability of encorafenib as single agent or in combination with binimetinib is well-established in studies outside China. The overall safety profile of encorafenib is consistent with the respective mechanism of action and the known profile

	
of BRAF inhibitors. The differentiated efficacy and safety profile of encorafenib is attributable to its substantially longer dissociation half-life ($T_{1/2\text{diss}}$).
 
No targeted therapy for the treatment of BRAF V600E mutant NSCLC has been approved in China and and vemurafenib is the only molecular-targeted drug approved for the treatment of patients with BRAF V600E mutant melanoma. Chemotherapy and immunotherapy (the same as that for melanoma and NSCLC without oncogenic driver mutations) remain the standard treatment in China, depending on the accessibility and affordability of these drugs. There is therefore an urgent medical need for targeted therapy for Chinese melanoma and NSCLC patients with BRAF V600E mutation in the era of personalized healthcare.
 
Limited clinical data of encorafenib monotherapy (or in combination with binimetinib) are available specifically in Chinese BRAF V600E mutant patients. This study therefore aims to provide additional clinical safety and tolerability data with encorafenib monotherapy in Chinese patients with BRAF V600E mutant melanoma or NSCLC to support further clinical development in combination with binimetinib.

Objectives and Endpoints	Endpoints
Primary	

 • To assess the safety of encorafenib 300 mg QD in monotherapy during Cycle 1. 	
 • Incidence of DLTs experienced during Cycle 1 (Days 1 to 28)
Secondary	

 • To characterize the safety and tolerability of encorafenib 300 mg QD in monotherapy in Chinese participants. • To provide PK data of encorafenib and its metabolite (LHY746) in monotherapy. 	
 • Incidence, nature and severity of TEAEs graded as per NCI CTCAE Version 4.03, TEAEs leading to dose interruption, reduction and discontinuation, treatment-emergent SAEs and deaths • Changes in clinical laboratory parameters, vital signs, ECGs • Incidence of targeted TEAEs of special interest • PK parameters of encorafenib and its metabolite (LHY746) after single and repeated administration

Abbreviations: DLT = dose limiting toxicity; ECG = electrocardiogram; NCI CTCAE = National Cancer Institute Common Terminology Criteria for Adverse Events; PK = pharmacokinetics; QD = once daily; SAE = serious adverse event; TEAE = treatment emergent adverse event.
	
Overall Design:	
This is a phase 1, multicenter, open-label, single-arm study to investigate the safety and tolerability of encorafenib 300 mg once daily (QD) monotherapy in adult Chinese participants with BRAF V600E mutant advanced solid tumors (unresectable metastatic melanoma or metastatic NSCLC), who are BRAF-inhibitor treatment-naïve and have failed the previous therapy(ies) for advanced metastatic disease or are not eligible to standard therapy. Participants will be eligible for the study based on identification of a BRAF V600E mutation in tumor tissue by a local National Medical Products Administration (NMPA) approved assay obtained prior to screening.
 
A dose limiting toxicity (DLT) is defined as any adverse event or abnormal laboratory value assessed as unrelated to disease, disease progression, intercurrent illness or concomitant medications/therapies resulting in the inability to tolerate at least 75% dose

	
intensity [(administered dose in mg/planned dose in mg) × 100] occurring within the first 28 days of study treatment (Cycle 1) that satisfies at least one of the predefined DLT criteria.
 
It is planned to enrol up to six evaluable participants using a 3+3 design. To be evaluable for tolerability assessment, participants must have either experienced an event meeting the DLT criteria in Cycle 1 or completed at least one cycle of study treatment and received at least 75% of the encorafenib dose intensity in Cycle 1. Non-evaluable participants, including withdrawals during Cycle 1 for reasons other than a DLT, will be replaced.
 
 • Three participants will initially be enrolled and receive encorafenib 300 mg QD, and will be evaluated for DLTs during the first cycle of treatment (28 days) [the DLT evaluation period]: 
 – If there are no DLTs in the first three participants in the DLT evaluation period, enrollment will be stopped. – If one of the first three participants experiences a DLT in the DLT evaluation period, a Trial Steering Committee (TSC) will make the recommendation whether three additional participants will be enrolled to expand the number of participants to a total of six. – If more than one of the first three treated participants experience a DLT, enrollment will be stopped. • If the group is expanded and two or more of the six participants experience a DLT, enrollment will be stopped.
Study Principal Investigator:	PII [REDACTED]
Number of participants	Up to 6 evaluable participants will be enrolled in the study which will be conducted at two or three sites in mainland China.
Treatment group and duration	
Encorafenib will be administered as a fixed, flat oral dose of 300 mg QD.
 
Study treatment will be administered in 28-day cycles until death, disease progression or one of the other predefined criteria for study treatment discontinuation is met.
 
 • If the study treatment is discontinued, the participant will have an end of treatment visit followed by a 30-day safety follow-up assessment 
Recruitment duration: 6 months.
 
Estimated duration of the follow-up period after last participant in: approximately 6 months.

Trial Steering Committee:	The trial steering committee (TSC) will analyse the available safety data and assess the toxicities as significant or not once the first three participants (and six participants if required) have fully completed the first cycle of treatment (28 days). The TSC will determine if encorafenib 300 mg QD is tolerable based on the DLT rate (DLTs observed

	
in <33% of participants) and evaluation of the overall toxicity profile (based on deaths, treatment emergent SAEs, treatment emergent adverse events (TEAEs) leading to discontinuation and to dose interruption/reduction).
 
The TSC will make a recommendation if the dose of encorafenib 300 mg QD is not deemed tolerable.

--	--

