2.1.4. Encorafenib Therapy

Encorafenib is a potent and highly selective adenosine triphosphate (ATP)-competitive small molecule inhibitor of *BRAF* V600 mutant kinase. Encorafenib suppresses the RAS/RAF/MEK/ERK pathway in tumor cell expressing *BRAF* V600 mutation.

In a first-in-human phase 1 dose escalation and dose expansion study (CLGX818X2101), 54 participants with locally advanced or metastatic *BRAF* V600 mutant melanoma initially received doses of encorafenib from 50 to 700 mg once daily (QD) or 75 to 150 mg twice daily. Dose limiting toxicities (DLTs) were reported in seven participants across the dose groups and were hand-foot skin reaction (HFSR), foot pain, fatigue, insomnia/asthenia, diarrhea/rash, facial paresis/confusion, and pain/neuralgia. All DLTs were reversible. The most common adverse events suspected to be related to encorafenib were cutaneous (rash, dry skin, HFSR, pruritus, keratosis pilaris, alopecia), pain in extremity, arthralgia, and fatigue. On the basis of the Bayesian model, the maximum tolerated dose (MTD) of encorafenib monotherapy was declared as 450 mg QD [Dummer 2013]. A further 33 participants were treated in the dose expansion phase; nine (33.3%) participants with melanoma and three (17.6%) participants with mCRC experienced at least one DLT during the first 28 days of treatment. The most common DLTs ($\geq 5\%$) observed in participants with melanoma treated at the MTD in the dose expansion phase were myalgia (33.3%), arthralgia (26.7%), fatigue (20.0%), asthenia (13.3%), and VIIth nerve paralysis and insomnia (6.7% each). Seven of the nine participants with a DLT required a dose reduction to 300 mg QD. Based on the early occurrence of these toxicities leading to dose reduction, the 300 mg QD dose was declared the recommended phase 2 dose (RP2D) for encorafenib monotherapy. The ORR for BRAF inhibitor-naïve and BRAF inhibitor-pretreated participants was 60.0% and 10.3% in the dose escalation phase and 60.0% and 22.2% in the dose expansion phase. Progression-free survival and OS were assessed for participants in the dose expansion phase only. Median PFS was 12.4 months (95% CI: 7.4–not reached) and 1.9 months (95% CI: 0.9–3.7) for BRAF inhibitor-naïve patients and BRAF inhibitor-pretreated participants. Median OS was not reached for BRAF inhibitor-naïve patients and was 9.7 months (95% CI: 3.68–10.84) for BRAF inhibitor-pretreated participants [Delord 2017].

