4.1.1. Study Design Overview

This is a phase 1, multicenter, open-label, single-arm study to investigate the safety and tolerability of encorafenib monotherapy in adult Chinese participants with *BRAF* V600E mutant advanced solid tumors (unresectable metastatic melanoma or metastatic NSCLC) who are *BRAF*- and *MEK*-inhibitor treatment-naïve and have failed the previous therapy(ies) for advanced metastatic disease or are not eligible to standard therapy. Participants will be eligible for the study based on identification of a *BRAF* V600E mutation in tumor tissue by a local National Medical Products Administration (NMPA) approved assay obtained prior to screening.

All participants will receive a fixed flat oral dose of 300 mg encorafenib QD.

It is planned to enrol up to six evaluable participants using a 3+3 design, shown in Figure 1.

Figure 1: Schema of 3+3 Design

Abbreviations: DLT = dose limiting toxicity; TSC = Trial Steering Committee

- Three participants will initially be enrolled and will be evaluated for DLTs during the first cycle of treatment (28 days) [the DLT evaluation period]:

- If there are no DLTs in the first three participants in the DLT evaluation period, enrollment will be stopped.
- If one of the first three participants experiences a DLT in the DLT evaluation period, a Trial Steering Committee (TSC) will make the recommendation whether three additional participants will be enrolled to expand the number of participants to a total of six.
- If more than one of the first three treated participants experience a DLT, enrollment will be stopped.
- If the group is expanded and two or more of the six participants experience a DLT, enrollment will be stopped.

A DLT is defined as any adverse event or abnormal laboratory value assessed as unrelated to disease, disease progression, intercurrent illness or concomitant medications/therapies that satisfies at least one of the criteria listed in **Table 4**.

Table 4: Criteria for Defining Dose Limiting Toxicities

Toxicity		Any of the following criteria
Blood and lymphatic system disorders[a]		≥Grade 3 neutropenia (ANC <1.0 × 10 ⁹ /L) for >7 consecutive days
		≥Grade 3 thrombocytopenia (platelets <50 × 10 ⁹ /L) for >7 consecutive days
		Grade 4 thrombocytopenia
		Febrile neutropenia (ANC < 1.0 × 10 ⁹ /L with fever ≥38.5°C)
Investigations (renal)		≥Grade 3 serum creatinine
Investigations (hepatic)		≥Grade 3 blood bilirubin (> 3 × ULN)
		≥Grade 3 ALT or AST for > 7 consecutive days

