		Grade 4 ALT or AST
		≥Grade 3 ALT or AST and ≥Grade 2 blood bilirubin
Investigations (metabolic)		Grade 3 lipase for >7 consecutive days
		Grade 4 lipase
Cardiac disorders		≥Grade 3
Gastrointestinal disorders		≥Grade 3 vomiting or nausea lasting more than 48 hours despite optimal antiemetic therapy[b]
		≥Grade 3 diarrhea lasting more than 48 hours despite optimal treatment
		≥Grade 3 pancreatitis
Skin and subcutaneous tissue disorders[c]: rash, photosensitivity or HFSR		Grade 3 rash/photosensitivity/HFSR for >7 consecutive days despite skin toxicity treatment (as per local practice)
		Grade 4 rash/photosensitivity/HFSR
General disorders and administration site conditions		Grade 3 fatigue/asthenia for >7 consecutive days
Ophthalmologic	Uveitis	Grade 3 for >21 consecutive days confirmed by ophthalmologic examination

Toxicity		Any of the following criteria
		Grade 4 confirmed by ophthalmologic examination
Any other eye disorders	Grade 3 for >21 consecutive days	
	Grade 4	
Other adverse events[d]		≥Grade 3 adverse events (excluding SCC)

Abbreviations: ALT = alanine aminotransferase; ANC = absolute neutrophil count; AST = aspartate aminotransferase; DLT = limiting dose toxicity; HFSR = hand-foot skin reaction (also known as palmar-plantar erythrodysesthesia [PPE] syndrome); NCI CTCAE = National Cancer Institute Common Terminology Criteria for Adverse Events; ULN = Upper limit of normal.

Grades according to NCI CTCAE grading system.

- [a] ≥Grade 3 anemia will not be considered a DLT unless judged to be a hemolytic process secondary to study treatment. ≥Grade 3 lymphopenia will not to be considered a DLT unless clinically significant.
- [b] Optimal therapy for vomiting or diarrhea will be based on study site guidelines with consideration of the prohibited medications listed in this protocol.
- [c] Squamous cell carcinoma reported to be an on-target side-effect that was manageable will not be considered a DLT.
- [d] An adverse event must be clinically significant to be defined as a DLT: alopecia, study treatment-related fever, electrolyte abnormalities (including K, NA, Cl, HCO₃, Mg, Ca, PO₄) that are ≤Grade 3 abnormalities will not be considered a DLT unless clinically significant.

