To be evaluable for tolerability assessment by the TSC, participants must have *either* experienced an event meeting the DLT criteria during Cycle 1 *or* completed at least one cycle of study treatment and received at least 75% of the encorafenib dose intensity (administered dose in mg/planned dose in mg) in Cycle 1³.

Participants who terminate study participation for any reason other than an adverse event or abnormal laboratory value related to disease, disease progression, intercurrent illness or concomitant medications/therapies before having received at least the encorafenib dose intensity of 75% (administered dose in mg/planned dose in mg) in Cycle 1 will be considered ineligible for the safety assessment required for tolerability and will be replaced.

The TSC will analyse the available safety data and assess the toxicities as significant or not once the first three participants (and six participants if required) have fully completed the first cycle of treatment (28 days). The TSC will determine if encorafenib 300 mg QD is tolerable based on the DLT rate (DLTs observed in <33% of participants) and evaluation of the overall toxicity profile (based on deaths, treatment emergent SAEs, treatment emergent adverse events (TEAEs) leading to discontinuation and to dose interruption/reduction).

The TSC will make a recommendation if the dose of encorafenib 300 mg QD is not deemed tolerable.

³ Participants who require a dose interruption or reduction during Cycle 1 will remain evaluable for tolerability decisions if the reason for the reduction and/or interruption represents a DLT.

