9.2. Sample Size Determination

The planned sample size is up to six evaluable participants based on a 3+3 design (see Section 4.1.1). No formal sample size calculation has therefore been performed and sample size is based upon empirical considerations.

Participants will receive encorafenib 300 mg QD. This dose will be considered acceptable if the observed Cycle 1 DLT rate in evaluable participants is <33% (e.g. less than one participant with DLTs out of three participants or less than two participants with DLTs out of six participants). To be evaluable, participants must have *either* experienced an event meeting the DLT criteria in Cycle 1 *or* completed at least one cycle of study treatment and received at least 75% of the encorafenib dose intensity (administered dose in mg/planned dose in mg) in Cycle 1 (see Section 4.1.1).

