5.3.1. Definition of Endpoint(s)

A DLT is defined as any adverse event or abnormal laboratory value assessed as unrelated to disease, disease progression, intercurrent illness or concomitant medications/therapies that satisfies at least one of the criteria listed in Table 2 (see Section 1.2).

DLTs will be identified using the DLT flag reported in the Adverse Event CRF form.

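### The synopsis adds a 75% dose-intensity condition to the DLT definition that the protocol body and SAP do not contain, so a site using it would leave some Table 4 DLTs unflagged

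*Protocol*

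**What the plan says.** The synopsis (Protocol 1.1, Overall Design) defines a DLT as an adverse event or abnormal laboratory value, not attributed to a list of other causes, "resulting in the inability to tolerate at least 75% dose" intensity. A bracket gives the ratio as administered over planned mg. The event must also fall in the first 28 days and meet at least one predefined criterion. All of these conditions apply jointly.

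Protocol 4.1.1 goes straight from the excluded causes to the criteria: "intercurrent illness or concomitant medications/therapies that satisfies at least one of the criteria listed in" Table 4. Protocol 9.4.2 and SAP 1.2 and 5.3.1 do the same (the SAP's copy is Table 2). None has a dose-intensity condition.

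Elsewhere the 75% figure serves only evaluability, replacement and the Dose-Determining Set (Protocol 4.1.1, 9.2 and 9.3; SAP 1.2, 3 and 4.2). For evaluability it is an alternative to having had a DLT. Footnote 3 of 4.1.1, also an evaluability rule, says that participants with a Cycle 1 interruption or reduction "will remain evaluable for tolerability decisions if the reason for the reduction and/or interruption represents a DLT", with no dose threshold attached.

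For the analysis, SAP 5.3.1 states: "DLTs will be identified using the DLT flag reported in the Adverse Event CRF form". SAP 5.3.3 plans no sensitivity analysis. Protocol 9.2 calls the dose acceptable if the observed DLT rate is below 33%, which it spells out as "less than one participant with DLTs out of three participants or less than two participants with DLTs out of six participants".

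**The concern.** On the bracketed ratio, a participant who receives at least 75% of the planned Cycle 1 dose cannot have a DLT under the synopsis, whatever Table 4 criterion was met. That participant also completes the cycle above the evaluability threshold, so stays in the denominator as DLT-free.

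The clause does not look like a slip to someone reading the synopsis. The next paragraph makes participants evaluable through either a DLT or a completed cycle at 75% or more, and the two routes appear to fit together. Neither document states which section prevails.

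DLT incidence is the only primary endpoint and the only numerical criterion the TSC has. With three or six participants, one event decides which side of the boundary the result falls on.

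**Working it through.** **Inputs.** Dose 300 mg once daily in 28-day cycles (synopsis). Planned Cycle 1 dose 28 × 300 = 8400 mg, the figure SAP 5.6.1 also uses. First reduced dose level 225 mg (Table 7). Handling of Grade 3 events from Table 19 (Appendix 4). DLT criteria from Table 4.

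**The plan's own boundary.** 0/3 = 0% (acceptable); 1/3 = 33.3% (not below 33%); 1/6 = 16.7% (acceptable); 2/6 = 33.3% (not acceptable). This matches the counts in Protocol 9.2.

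**The threshold.** 75% of 8400 mg is 6300 mg, so intensity falls below 75% only if more than 2100 mg is lost, that is, more than seven full doses. A one-level reduction alone can never do this: 225/300 = 75%, even if taken on all 28 days.

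**Example 1.** Table 4 counts "Grade 3 diarrhea lasting more than 48 hours despite optimal treatment" (or a higher grade). Table 19 holds dosing until Grade 1 or lower and resumes one level down if the event is related. Onset Day 15, held 3 days, then 225 mg:

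(14 × 300 + 3 × 0 + 11 × 225) / 8400 = 6675 / 8400 = 79.5%.

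**Example 2.** Arthralgia has no row of its own in Table 4. A clinically significant Grade 3 case falls under the row for other adverse events, which has no duration requirement. Onset Day 12, held 3 days, then 225 mg:

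(11 × 300 + 3 × 0 + 14 × 225) / 8400 = 6450 / 8400 = 76.8%.

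Both are DLTs under Table 4 and neither is under the synopsis. Protocol 2.1.4 reports myalgia and arthralgia as the most common DLTs in the melanoma expansion of the first-in-human study. That was at 450 mg, so it supports the type of event and not its frequency at 300 mg.

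**General condition.** For a hold of *h* days from Day *d*, then 225 mg to Day 28, the dose lost is 300*h* + 75(29 − *d* − *h*) mg. Requiring this to be at most 2100 mg gives *d* ≥ 3*h* + 1.

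| Hold | From Day | Cycle 1 intensity |
|---|---|---|
| 1 day | 4 | 75.0% |
| 3 days | 10 | 75.0% |
| 5 days | 16 | 75.0% |
| 3 days | 9 | 74.1% |
| 3 days | 5 | 70.5% |

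A hold that starts on Day 22 or later also leaves at least 21/28 = 75.0%.

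**Left out of the count.** Table 4 rows that require more than 7 or more than 21 consecutive days are not counted; an 8-day hold alone gives 20/28 = 71.4%. Permanent discontinuation is not counted either, because failure to tolerate the dose could be read as met there.

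**Effect of one unflagged event.** At three participants, 33.3% becomes 0%: the TSC no longer considers expansion and enrollment stops with the dose acceptable on DLT rate. At six, 33.3% becomes 16.7%, from not acceptable to acceptable.

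**The case against.** The strongest reply is that this is an editorial mismatch. Every operative definition agrees and omits the clause, 9.4.2 refers back to 4.1.1, and the CRF-flag sentence in SAP 5.3.1 directly follows the Table 2 definition. The synopsis lists no criteria, so a site must open Table 4, which sits under the definition without the clause. Flagging instructions may be in the eCRF user guide, and sites are trained on the protocol at initiation. The TSC weighs adverse events that lead to interruption or reduction, and both examples involve both. SAP 5.6.2 lists Grade 3 and 4 events and events leading to dose modification. With at most six evaluable participants, such an event would be visible.

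Most of this stands. The harm is conditional on a site importing the synopsis clause, the documents do not show that any site would, and the TSC has a real chance of noticing the event. It is also fair that the bracketed ratio names no period and that footnote 3 is an evaluability rule, not a second definition of a DLT.

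It does not dispose of the point. The conflict is in the definition of the sole primary endpoint, nothing says which text prevails, and the SAP's primary table counts the flag and nothing else. A TSC that noticed the event could temper its recommendation, but the reported DLT rate would still be wrong.

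**Conclusion.** The concern holds and should be fixed. The synopsis sets a stricter DLT definition than Protocol 4.1.1 and 9.4.2 and SAP 1.2 and 5.3.1. Where it is applied, Table 4 events with a short or late hold go unflagged while the participant remains in the denominator. One such event crosses the acceptability boundary at either stage (1/3 to 0/3, or 2/6 to 1/6).

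This rests on three assumptions: a site sets the flag from the synopsis wording, the ratio is taken over Cycle 1 against 8400 mg, and dosing follows Table 19 with resumption at 225 mg. The documents do not give the share of DLTs that would be lost, so no change in the probability of accepting the dose is claimed. The mismatch is certain; its effect on the result is conditional.

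**What to change.** In the synopsis DLT definition, delete the clause that begins "resulting in the inability to tolerate at least 75% dose", through the end of the bracketed ratio, so that it matches Protocol 4.1.1 and 9.4.2 and SAP 1.2 and 5.3.1. Keep 75% dose intensity for evaluability, replacement and the Dose-Determining Set only. Confirm in writing to sites that Section 4.1.1 and Table 4 govern the CRF DLT flag, and re-check any flags already set against Table 4.

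The cost is a one-sentence protocol correction, with whatever ethics committee approval Appendix 1 (10.1.1) requires for an amendment, plus a site clarification letter. The operative definition and the SAP text stay as they are, and no extra data are needed.
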